## 8.3 Definition of an Adverse Event

An *adverse event* (AE) is any untoward, undesired, or unplanned clinical event in the form of signs, symptoms, disease, or laboratory or physiological observations occurring in a subject participating in a clinical study with the Sponsor's investigational product, regardless of causal relationship. Adverse events will include any conditions that: 1) were not present prior to investigational product administration, but appeared following investigational product administration, but worsened in severity and/or frequency following investigational product administration.

Adverse events will be noted in the study records and on the case report form with a full description including the nature, date of onset (as well as time, if feasible), determination of non-serious versus serious, intensity (mild, moderate, severe, life-threatening, death), duration (*i.e.* end date and time, if feasible), causality, and outcome of the event.

*Suspected adverse reaction* (SAR) means any adverse event for which there is a reasonable possibility that the drug caused the adverse event. For the purposes of IND safety reporting, reasonable possibility means there is evidence to suggest a causal relationship between the intervention and the adverse event. Suspected adverse reaction implies a lesser degree of certainty than adverse reaction, which means any adverse event caused by a drug. Suspected adverse reactions are the subset of all AEs for which there is a reasonable possibility that the drug caused the event. Inherent in this definition, and in the requirement to report them is the need for the sponsor to evaluate the available evidence and make a judgment about the likelihood that the drug actually caused the adverse event.

An AE or SAR is considered unexpected if it is not listed in the Investigator's Brochure or is not listed at the specificity or severity that has been observed.

#### 8.4 Definition of a Serious Adverse Event (SAE)

An AE or SAR is considered serious if, in the view of either the Investigator or Sponsor, it results in any of the following outcomes:

- Death;
- A life-threatening event (its occurrence places the subject at immediate risk of death);
- Inpatient hospitalization or prolongation of existing hospitalization;
- A persistent or significant incapacity or substantial disruption of the ability to conduct normal life functions; or
- A congenital anomaly/birth defect.

Important medical events that may not result in death, be life-threatening, or require hospitalization may be considered serious when, based upon appropriate medical judgment,

they may jeopardize the subject and may require medical or surgical intervention to prevent one of the outcomes listed in this definition.

A prescheduled, elective procedure, or a routinely scheduled treatment that requires hospitalization is NOT considered as to be an SAE; the study site must document all of the following:

- The prescheduled, or elective procedure, or routinely scheduled treatment was scheduled (or was on a waiting list to be scheduled) prior to obtaining the subject's consent to participate in the study.
- The condition requiring the prescheduled, or elective procedure, or routinely scheduled treatment was present before and did not worsen or progress, in the opinion of the Investigator, between the subject's consent to participate in the study and the time of the procedure or treatment. The prescheduled, or elective procedure, or routinely scheduled treatment is the sole reason for the intervention or hospital admission.

A distinction should be drawn between serious and severe events or reactions. A severe AE/SAR is a major event of its type. A severe AE/SAR does not necessarily need to be considered serious. For example, nausea which persists for several hours may be considered severe nausea, but would not be considered serious. On the other hand, a stroke that results in only a limited degree of disability may be considered a mild stroke, but would be considered serious.

If there is any doubt whether an AE qualifies as an SAE based on the definitions above, the Investigator should contact the Sponsor.

#### 8.5 Grading of Adverse Events

Adverse events will be graded for intensity as mild, moderate, severe, life-threatening, or resulting in death as defined below. If applicable, the toxicity grade found in the Manual of Procedures should also be noted.

Grade	Description
Mild	Symptom barely noticeable to the subject and does not influence his/her performance or functioning.
Moderate	Symptom of a sufficient severity to make the subject uncomfortable or hinder the performance of daily activities; treatment of symptom may be needed.
Severe	Symptom causes severe discomfort; treatment for symptom may be given and/or subject may be hospitalized.
Life- threatening	Occurrence of the event places the subject at immediate risk of death.
Death	Occurrence of the event results in the death of the subject.

#### 8.6 Relationship to the Investigational Product

The Investigator will document his/her opinion of the relationship of each AE to the vector administration procedure, investigational product, and study measures using the criteria outlined below. Relationship to the administration procedure should also be noted.

Relationship	Description
Unlikely to be related	AEs which, after careful medical consideration at the time they are evaluated, are judged to be unrelated to the investigational material because:
	a) AE does not follow a reasonable temporal sequence or known pattern of response after administration of the investigational material
	b) AE could readily have been produced by the subject's clinical state, environmental or toxic factors, or other modes of therapy administered to the subject.
Possibly related	AEs for which, after careful medical consideration at the time they are evaluated, a connection with the investigational material appears unlikely but cannot be ruled out with certainty, because at least one of the following criteria are met:
	a) AE follows a reasonable temporal sequence or known pattern of response after administration of investigational material.
	b) AE could not readily have been produced by subject's clinical state, toxic or environmental factors or other modes of therapy administered to the subject.
Probably related	AEs which, after careful medical consideration at the time they are evaluated, are felt with a high degree of certainty to be related to the investigational material, because the following criteria are met:
	a) AE cannot be reasonably explained by the known characteristics of the subject's clinical state or by environmental or toxic factors;
	and at least one of the following is true:
	b) AE follows a reasonable temporal sequence from administration of the investigational new drug and/or administration procedure;
	c) AE follows a known pattern of response to the investigational new drug or administration procedure;
	d) AE disappears or decreases on cessation or reduction in activity of the investigational new drug; or
	e) AE reappears upon re-challenge or re-administration of the investigational new drug.

Investigators are responsible for reporting SAEs and suspected unexpected serious adverse reactions (*i.e.*, SUSARs) to their respective Independent Reviewing Authorities (IRAs; may

also be known as Institutional Review Boards or Independent Ethics Committees) in accordance with local reporting requirements.

#### 8.7 Other Reportable Events

Certain events that occur in the absence of an AE should be reported to Spark Therapeutics as other reportable events. The events will be recorded using the Other Reportable Information Form provided by the Sponsor. These include the following:

- Accidental exposure (someone other than the study subject was exposed to investigational product)
- Overdose (subject received more than the intended dose of investigational product)
- Other medication errors that potentially place subjects at a greater risk of harm than was previously known or recognized (*e.g.* investigational product was administered by an incorrect route).

#### 8.8 Reporting Timeframes

The Investigators are responsible for notifying the Sponsor or designee of all AEs, other unanticipated problems related to research, and pregnancy occurrences and outcomes in accordance with the following timeline:

Type of AE	Initial Notification (Phone, Email)	Written Report
All serious AEs, including serious SARs	24 hours	The investigator (or delegate) must submit the SAE report forms (initial and follow-up) within 24 hours to the Sponsor/designee. Local telephone and fax number for reporting from each specific participating country is provided in the Investigator Study Manual. If the minimum requirements for reporting are known, the investigator should notify Spark immediately and not wait for additional information to fully document the event. Follow-up reports will be submitted by the investigator to Spark at appropriate intervals until the SAE has resolved or, in the case of permanent impairment, until it has stabilized.
Other unanticipated problems or reportable events related to research and pregnancy occurrences and outcomes	N/A	Within 5 business days
All other AEs	N/A	Summary of AEs reported at time of continuing review As needed for sponsor reporting requirements (FDA & NIH/OBA annual reports and DSMB reports) or as specified in MOP

All AEs must be entered in the appropriate section of the CRF. To improve the quality and consistency of AE data, Investigators should observe the following general guidelines:

• Standard English medical terminology should be used rather than colloquial expressions or abbreviations.

- Whenever possible, the AE should be evaluated and reported as a diagnosis rather than as individual signs or symptoms. If a definitive diagnosis is not possible, the individual signs and symptoms should be recorded.
- If an AE requires a surgical or diagnostic procedure, the illness leading to the procedure should be recorded as the AE, not the procedure itself.

For SAEs, the initial notification should include all available information requested on the SAE Form; the initial notification must be followed by written documentation, which includes all information including causality assessment from the Principle Investigator. The SAE Form will collect data surrounding the event, *e.g.*, the nature of the symptom(s), time of onset in relation to initiation of investigational product, duration, severity, and whether or not treatment was administered for the symptoms experienced. The Investigator's assessment of the probable cause of the event will also be included. A physician will examine subjects who experience an SAE or a medical emergency situation as soon as possible. The physician in attendance will do whatever is medically necessary for the safety and well-being of the subject. The subject will remain under observation as long as medically indicated in the opinion of the Investigator. Appropriate lab studies will be conducted until all parameters return to normal or are otherwise explained. The SAE will be followed until resolved or until medically stabilized. In a medical emergency requiring immediate attention, study site staff will provide appropriate medical care, according to current standards of care. The Investigator or his/her designee should contact the Sponsor or designee Medical Monitor. The Sponsor or designee will notify the appropriate federal regulatory authorities.

If an SAE has not resolved at the time of the initial report, a follow-up report including all relevant new or reassessed information (*e.g.*, concomitant medication, medical history) should be submitted to the Sponsor or designee. All SAEs should be followed until either resolved or stable. The Medical Monitor and the independent DSMB will review all AEs.

Investigator safety reports must be prepared for suspected unexpected serious adverse reactions (SUSARs) according to local regulatory requirements and Sponsor policy, and forwarded to Investigators as necessary. An Investigator who receives an investigator safety report describing an SAE or who receives other specific safety information (e.g., summary or listing of SAEs) from the Sponsor will review and then file it along with the Investigator's Brochure and will notify the IRB/IEC if appropriate according to local regulatory reporting requirements.

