## 7.4 Stopping Rules

The toxicity criteria are based on the WHO toxicity scale, with added assessments pertaining to ocular AEs (located in the Manual of Procedures). Dose-limiting toxicity (DLT) will be defined as any irreversible Grade 3 or higher toxicity, or any reversible Grade 4 toxicity, that is possibly or probably related to AAV2-hCHM. Irreversible toxicities are defined as those that persist at the same (or higher) grade for more than seven days; reversible toxicities are those resolving in seven or fewer days.

If DLT is experienced, further subject enrollment will be delayed pending consultation with the DSMB. If a subject experiences any DLT, the DSMB will assist in determining whether additional subjects should be enrolled at the same dose level, or at a lower dose level. If two subjects of a dose group develop limiting toxicity, possibly or probably attributable to the vector, the maximum tolerated dose (MTD) will have been reached. In the event this occurs in Dose Group 2, additional subjects may be enrolled to the group just below the MTD, *i.e.* Dose Group 1.

If a single occurrence of Grade 4 toxicity, excluding toxicities covered under the category "General", or death of a subject occurs and is deemed possibly or probably related to the AAV2-hCHM, the Sponsor will halt enrollment and notify the DSMB and FDA. Further enrollment and/or vector administrations will be conducted only after FDA and the Sponsor confer to determine that the IND is not on clinical hold, and the DSMB agrees to continue enrollment. Study visits for subjects that have already received AAV2-hCHM will continue per protocol.

The Sponsor or designee will report all SAEs and AEs to the DSMB, FDA, NIH OBA, and to Principal Investigators (who will in turn notify the IRBs/Institutional Ethics Committees (IECs) of record) within the required reporting timeframes. In addition to the stopping rules outlined above and based on the toxicity criteria table (located in the Manual of Procedures), the Sponsor will respond to recommendations of the DSMB.

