#### 8.2 Adverse Event Reporting

All events described by the subject will be reported as AEs, regardless of toxicity grade in.

Protocol-defined safety laboratory test results will be collected prospectively and analyzed separately as part of the study. Additional laboratory test results at other time points may be available to the Investigators as part of standard clinical practice. Throughout the active phase of the study, laboratory-related abnormalities should be recorded as AEs only if considered clinically significant, outside the range of expected values given the subject's baseline assessments and clinical course, and not known to be part of another AE diagnosis. As per regulatory guidelines, pre-existing conditions, including abnormal lab values manifest at baseline testing, will only be reported as adverse events if the condition worsens in severity and/or frequency.

The Investigators will follow an AE until the event is either resolved or assessed as stable.

The Investigators are responsible for notifying the Sponsor representative or designee and the IRB of all AEs and other unanticipated problems related to research. Unanticipated problems are other types of incidents, experiences, and outcomes that occur during the conduct of human subject research that are not considered adverse events. For example, some unanticipated problems involve social or economic harm instead of the physical or psychological harm associated with adverse events. In other cases, unanticipated problems place subjects or others at increased *risk* of harm, but no harm occurs.

The Sponsor or designee will notify the appropriate federal regulatory authorities (FDA, NIH OBA, DSMB). Events that do not require expedited reporting will be summarized at the time of continuing review / annual report.

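### Enrollment pauses on toxicity grade, but prompt site reporting depends on seriousness, so the sponsor may learn too late of a dose-limiting toxicity that is not serious

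*Protocol*

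**What the plan says.** **The pausing rule (Protocol 7.4).** "Dose-limiting toxicity (DLT) will be defined as any irreversible Grade 3 or higher toxicity, or any reversible Grade 4 toxicity", provided it is possibly or probably related to AAV2-hCHM. On persistence: "Irreversible toxicities are defined as those that persist at the same (or higher) grade for more than seven days". The consequence: "If DLT is experienced, further subject enrollment will be delayed pending consultation with the DSMB". Separately, a single related Grade 4 event outside the General category, or a related death, makes the sponsor halt enrollment. Seriousness is not part of the DLT definition, and 7.4 gives the site no time limit for telling anyone.

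**The reporting timeline (Protocol 8.8).** The 24-hour row is for "All serious AEs, including serious SARs". A five-business-day row covers pregnancies, other reportable events and unanticipated problems. Section 8.2 defines unanticipated problems as things that are not adverse events, and 8.7 describes other reportable events as occurring without an AE. For all other AEs, initial notification is not applicable. The written report is "Summary of AEs reported at time of continuing review", or as needed for sponsor and DSMB reports, or as the Manual of Procedures (MOP) specifies. Section 8.2 agrees: "Events that do not require expedited reporting will be summarized at the time of continuing review / annual report".

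**Severity and seriousness (Protocol 8.4).** "A severe AE/SAR does not necessarily need to be considered serious". Important medical events may be judged serious when "they may jeopardize the subject and may require medical or surgical intervention to prevent one of the outcomes listed in this definition".

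**The concern.** The event that should pause the trial is identified on one scale, and the duty to report promptly is set on another. A related Grade 3 event that lasts more than seven days and is managed without admission can be a DLT and still not be an SAE. It then falls in the slowest row of the table.

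The sponsor and the DSMB can act only on what they know, and a second site cannot wait for an event it has not heard of. The Protocol synopsis makes limiting toxicity the primary statistical endpoint, and 4.4 acknowledges that the treatment cannot practically be withdrawn. Late notice could therefore mean that further subjects receive an irreversible administration at the same dose while a qualifying event is known at only one site.

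**Working it through.** The documents give no figure on this point to reproduce. The check has two parts.

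**1. Is there another route with a deadline?**

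| Place | What it provides | Site deadline for a non-serious DLT |
|---|---|---|
| Protocol 7.4 | Sponsor passes AEs on to the DSMB, FDA and investigators | None; concerns onward reporting |
| Protocol 8.2, 8.8 | Investigators notify the sponsor of all AEs | 8.8 ties this duty to its own table |
| Protocol 8.8 | All AEs entered in the CRF | None |
| Protocol 8.8 | Medical Monitor and DSMB review all AEs | None |
| Protocol 9.4.1 | DSMB meets at least annually during enrollment | None |
| SAP 4.1 | Remote data capture, full source verification | None |
| MOP | Named in the 8.8 cell | Unknown; not supplied |

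**2. How many further injections could precede the pause?**

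Inputs from the documents:
- Dose Group 2 has up to 10 subjects (Protocol 3.1).
- Injections are at least 14 days apart study-wide for the first two subjects, then at least 14 days apart per site (Protocol 3.2).
- Persistence must exceed 7 days (Protocol 7.4).

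Assumptions:
- The DLT is a Grade 3 event in the first subject of Dose Group 2, injected on day 0.
- Every injection slot is used.
- The number of sites is 1, 2 or 3. The SAP revision table records a site added for Dose Group 2, so at least two is a fair inference; the exact number is not given.
- Reporting lags are as shown below.

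Formulas:
- Day the DLT is met = onset day + 8.
- Day the sponsor knows = onset day + 8 + lag.
- Count = injections after the first subject, on or before the day the sponsor knows.

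Fastest calendars:
- One site: days 0, 14, 28, …, 126 (9 × 14 = 126).
- Two sites: days 0, 14, 14, 28, 28, 42, 42, 56, 56, 70.
- Three sites: day 0, then three on each of days 14, 28 and 42.

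| Onset day | DLT met | Lag | Sponsor knows | 1 site | 2 sites | 3 sites |
|---|---|---|---|---|---|---|
| 1 | 9 | 0 | 9 | 0 | 0 | 0 |
| 5 | 13 | 0 | 13 | 0 | 0 | 0 |
| 6 | 14 | 0 | 14 | 1 | 2 | 3 |
| 1 | 9 | 1 day | 10 | 0 | 0 | 0 |
| 5 | 13 | 1 day | 14 | 1 | 2 | 3 |
| 1 | 9 | 30 days | 39 | 2 | 4 | 6 |
| 5 | 13 | 30 days | 43 | 3 | 6 | 9 |
| 1 | 9 | 365 days | 374 | 9 | 9 | 9 |

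These counts assume that no site stops of its own accord. With two sites, if the site that saw the event holds its own injections, only the other site continues. With the 30-day lag that gives days 14 and 28 (2 subjects), or days 14, 28 and 42 (3 subjects).

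For onset on day 6 or later, an injection can precede the DLT call even with immediate reporting. That follows from the persistence rule and is not caused by 8.8.

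**The case against.** - **The Manual of Procedures.** The 8.8 cell ends by deferring to the MOP, which also holds the toxicity criteria. A faster route for graded toxicities may be there. This stands as a limit on certainty. However, 7.4 cites the MOP for toxicity criteria and not for notification times, so the link should be visible in the protocol either way.
- **The wording of the trigger.** Section 7.4 acts when a DLT is experienced, not when a report is filed, and 14-day spacing leaves room to act. This stands for early-onset events that are promptly known. It does not help a second site that has not been told.
- **Other channels.** CRF entry, medical monitoring, DSMB review and source verification may bring the event to light well before continuing review. They make a long silence less likely, but none has a stated time.
- **Many DLTs will be SAEs.** Life-threatening events and significant incapacity are serious, important medical events may be judged so, and in doubt the investigator should contact the sponsor. This stands. The gap is mainly persistent, non-serious Grade 3 events. Whether a non-serious Grade 4 event can arise depends on the scale in the MOP.
- **The escalation hold.** Dose Group 2 cannot open without DSMB approval after at least 30 days of Dose Group 1 data. This protects the step between groups, not subjects within Dose Group 2.
- **The calendar.** It assumes that every slot is filled. Protocol 7.3 states the two-week interval without a site limit; on that reading the one-site column applies however many sites are active.

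**Conclusion.** The mismatch between 7.4 and 8.8 is real. Enrollment is delayed or halted by grade, persistence and relatedness, while prompt notification follows seriousness, and no supplied text gives a non-serious DLT a deadline. The pausing rule may therefore act too late, chiefly within Dose Group 2.

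The size runs from 0 to 9 further subjects, depending on the assumed lag and number of sites. For onset on days 1 to 5, it is 0 with same-day knowledge and, with a 30-day lag, 2 to 3 at one site or 4 to 6 at two. Slower recruitment lowers these counts.

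A reader might infer that the rule can act only after further subjects have been injected, or that nine more injections are the expected result. The documents support neither. The rule can act first when an early event is known promptly. Nine requires notice to wait for an annual review, and the yearly interval is itself an assumption.

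This is a change the sponsor should make, subject to checking the MOP. If all injections are already complete, which the documents do not say, the benefit to later subjects in this trial falls.

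**What to change.** Add a row to the 8.8 table. Any AE possibly or probably related to AAV2-hCHM and graded 3 or higher on the MOP toxicity scale, serious or not, goes to the sponsor on the existing 24-hour route, with a follow-up report on whether it persists beyond seven days. Cross-refer to this row from 7.4. If the MOP already contains such a route, cite it in 7.4 and 8.8 instead.

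The first notice would then be due one day after a Grade 3 event is identified, about seven days before it could meet the persistence criterion (onset + 8 minus onset + 1). The follow-up report would settle its DLT status.

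The cost is one table row and a cross-reference in an amendment, plus a few expedited reports of Grade 3 events that resolve and never become DLTs. The DLT definition and the clinical rules stay as they are.

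Protocol 3.2 (interval per site after the first two subjects) and 7.3 (no site limit) state the injection interval differently, and SAP 3.1 and 3.2.3 repeat the difference. The sponsor should reconcile these passages, because the number of subjects exposed during any reporting lag depends on which applies.
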